- Collect samples of conjunctival (eye) secretions and saliva for HSV detection
- Obtain MRI scan
- Should a patient have an access device (eg., Rickham or Ommaya reservoir) that accesses either the more central portion of the tumor/cyst, or the CSF space, fluid will be aspirated as possible (expected, 2-10cc) from the catheter for laboratory studies. These specimens will be obtained at either the pre op clinic visit or the day of surgery, as well as up to daily during the inpatient hospitalization (per the surgeon's discretion), and again at post op visit day 10, Day 28, and Months 3,6,9 and 12

Months 4 and 5 (study coordinator visit):

- Review medications
- AE monitoring
- Collect blood for the following:
 - CBC with diff and platelets
 - Serum Chemistry (sodium, potassium, chloride, bicarbonate, glucose, BUN, creatinine, calcium, phosphorus, total protein, uric acid, GGT, AST/ALT, CK, LDH, alkaline phosphatase, total bilirubin, cholesterol, triglyceride)
 - PT/INR, PTT
 - HSV detection
- Collect samples of conjunctival (eye) secretions and saliva for HSV detection

Months 6 and 9:

- Review medications
- AE monitoring
- Obtain vital signs (pulse, blood pressure, respiratory rate, temperature and weight)
- Perform a complete physical exam
- Perform a neurological (nervous system) examination to include assessment of cranial nerve abnormalities, gait abnormalities (when appropriate), sensory abnormalities, muscle strength, and level of consciousness
- Complete the Karnofsky Performance Scale (KPS)
- Collect blood for the following:
 - CBC with diff and platelets
 - Serum Chemistry (sodium, potassium, chloride, bicarbonate, glucose, BUN, creatinine, calcium, phosphorus, total protein, uric acid, GGT, AST/ALT, CK, LDH, alkaline phosphatase, total bilirubin, cholesterol, triglyceride)
 - PT/INR, PTT
 - HSV antibody titer
 - HSV detection
 - IL-12 detection
 - LTA Elispot
 - IFN gamma assay
 - Immune studies - to be stored for future research
- Collect samples of conjunctival (eye) secretions and saliva for HSV detection
- Obtain MRI scan
- Should a patient have an access device (eg., Rickham or Ommaya reservoir) that accesses either the more central portion of the tumor/cyst, or the CSF space, fluid will be aspirated as possible (expected, 2-10cc) from the catheter for laboratory studies. These specimens will be obtained at either the pre op clinic visit or the day of surgery, as well as up to daily during the inpatient hospitalization (per the surgeon's discretion), and again at post op visit day 10, Day 28, and Months 3,6,9 and 12

Month 12 (end of study):

- Review medications
- AE monitoring
- Obtain vital signs (pulse, blood pressure, respiratory rate, temperature and weight)

- Perform a complete physical exam
- Perform a neurological (nervous system) examination to include assessment of cranial nerve abnormalities, gait abnormalities (when appropriate), sensory abnormalities, muscle strength, and level of consciousness
- Complete the Karnofsky Performance Scale (KPS)
- Collect blood for the following:
 - CBC with diff and platelets
 - Serum Chemistry (sodium, potassium, chloride, bicarbonate, glucose, BUN, creatinine, calcium, phosphorus, total protein, uric acid, GGT, AST/ALT, CK, LDH, alkaline phosphatase, total bilirubin, cholesterol, triglyceride)
 - PT/INR, PTT
 - HSV antibody titer
 - HSV detection
 - IL-12 detection
 - LTA Elispot
 - IFN gamma assay
 - Immune studies - to be stored for future research
- Collect samples of conjunctival (eye) secretions and saliva for HSV detection
- Obtain MRI scan
- Should a patient have an access device (eg., Rickham or Ommaya reservoir) that accesses either the more central portion of the tumor/cyst, or the CSF space, fluid will be aspirated as possible (expected, 2-10cc) from the catheter for laboratory studies. These specimens will be obtained at either the pre op clinic visit or the day of surgery, as well as up to daily during the inpatient hospitalization (per the surgeon's discretion), and again at post op visit day 10, Day 28, and Months 3,6,9 and 12

Unscheduled Visit:

- The following data will be collected at a standard of care follow-up visit only if it has been collected for standard of care purposes (that is: these procedures will not be conducted for research purposes only):
 - Collect vital signs (pulse, blood pressure, respiratory rate, temperature and weight), if done as SOC
 - Collect a complete physical exam data, if done as SOC
 - Perform a neurological (nervous system) examination to include assessment of cranial nerve abnormalities, gait abnormalities (when appropriate), sensory abnormalities, muscle strength, and level of consciousness, if done as SOC
 - Collect the Karnofsky Performance Scale (KPS), if done as SOC
 - Obtain MRI scan, if done as SOC
- The following procedures will be performed for research purposes only:
 - Review medications
 - AE monitoring
 - Collect samples of conjunctival (eye) secretions and saliva for HSV detection
 - Should a patient have an access device (eg., Rickham or Ommaya reservoir) that accesses either the more central portion of the tumor/cyst, or the CSF space, fluid will be aspirated as possible (expected, 2-10cc) from the catheter for laboratory studies. These specimens will be obtained at either the pre op clinic visit or the day of surgery, as well as up to daily during the inpatient hospitalization (per the surgeon's discretion), and again at post op visit day 10, Day 28, and Months 3,6,9 and 12
 - Collect blood for the following:
 - CBC with diff and platelets
 - Serum Chemistry (sodium, potassium, chloride, bicarbonate, glucose, BUN, creatinine, calcium, phosphorus, total protein, uric acid, GGT, AST/ALT, CK, LDH, alkaline phosphatase, total bilirubin, cholesterol, triglyceride)
 - PT/INR, PTT

- HSV antibody titer
- HSV detection
- IL-12 detection
- LTA Elispot
- IFN gamma assay
- Immune studies - to be stored for future research

9. MEASUREMENT OF EFFECT

Although response is not the primary endpoint of this trial, patients with measurable disease will be assessed by standard criteria.

9.1 Definitions

Although the Response Evaluation Criteria in Solid Tumors (RECIST) Committee has proposed new international criteria for the evaluation of response and progression of solid tumor, unidimensional measurements alone have not yet been sufficiently validated for the evaluation of malignant gliomas. The MacDonald criteria will be used for evaluation of treatment responses which is more appropriate for patients who have failed surgery, radiation and chemotherapy prior therapy than recently described RANO criteria which is more appropriate for newly diagnosed patients with high-grade, malignant brain tumors [39].

9.1.1 Measurable Disease

Measurable lesions are defined as those that can be accurately measured in at least one dimension (longest diameter to be recorded) as ≥ 10 mm with MRI scan. All intracranial malignant glioma is therefore measurable disease. All tumor measurements must be recorded in millimeters (or decimal fractions of centimeters).

9.1.2 Non-measurable Disease

This type of lesion is not applicable in this study.

9.1.3 Target Lesions

All intracranial lesions that are likely manifestations of the patient's malignancy will be considered target lesions.

9.1.4 Non-target Lesions

This type of lesion is not applicable in this study.

9.2 Guidelines for Evaluation of Measurable Disease

All measurements should be taken and recorded in metric notation using a ruler or calipers, or digitized method. All screening evaluations should be performed as closely as possible to the beginning of treatment and never more than 4 weeks before the beginning of the treatment.

Because all of the patients enrolled in this study will have received prior radiation therapy, tumor lesions that are situated in a previously irradiated area will be considered measurable.

The same method of assessment and the same technique should be used to characterize each identified and reported lesion at baseline and during follow-up. Imaging-based evaluation is the only means of assessing the antitumor effect of this treatment for this disease.

9.3 Response Criteria

The following criteria are based upon the volume changes that correspond to the definitions proposed by the MacDonald criteria. For the purposes of this study, the objective response of each patient's disease to M032 will be evaluated by the comparison of a baseline MRI scan to follow-up MRI. For those patients receiving intratumoral inoculation, the screening MRI will serve as the baseline MRI, and follow-up scans will be done at study Day 3, Day 28, Month 3, Month 6, Month 9 and Month 12. To prevent the introduction of observer bias, a software package which determines tumor areas and volumetrics via assessment of pixel intensity will be utilized to compare pre-and post-treatment images.

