3. PATIENT SELECTION

3.1 Eligibility Criteria

- 3.1.1 Patients must have histologically or cytologically confirmed *glioblastoma multiforme*, anaplastic astrocytoma, or gliosarcoma.

- 3.1.2 Prior therapy: Patients must have failed external beam radiotherapy to the brain, and if eligible and tolerated, undergone appropriate treatment with temozolomide chemotherapy. All radiation and additional chemotherapies must have been completed at least 4 weeks prior to enrollment. Prior therapy with nitrosoureas must have been completed at least 6 weeks prior to enrollment.
- 3.1.3 Age ≥ 18 years (age of majority for clinical trials in Alabama). Because no dosing or adverse event data are currently available on the use of M032 in patients < 18 years of age, children are excluded from this study but will be eligible for future pediatric phase 1 single-agent trials.
- 3.1.4 Karnofsky Performance Status (KPS) $\geq 70\%$ (see Appendix B).
- 3.1.5 Life expectancy of greater than 4 weeks.
- 3.1.6 Patients must have normal organ and marrow function as defined below:
- leukocytes..... $\geq 3,000/\mu\text{l}$
 - absolute neutrophil count..... $\geq 1,500/\mu\text{l}$
 - platelets..... $\geq 100,000/\mu\text{l}$
 - total bilirubin.....within normal institutional limits
 - AST(SGOT)/ALT(SGPT)..... ≤ 2.5 X institutional upper limit of normal
 - creatinine within normal institutional limits
- OR**
- creatinine clearance..... ≥ 60 mL/min/1.73 m² for patients with creatinine levels above institutional normal.
- 3.1.7 Residual lesion must be ≥ 1.0 cm and ≤ 5.5 cm in diameter without bilateral extension through the corpus callosum as determined by MRI as this is a locally delivered treatment. These parameters will be re-evaluated on imaging done on the day of catheter implantation and if the lesion no longer meets the criteria, the patient will not undergo catheter implantation or treatment with M032.

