4. TREATMENT PLAN

4.1 Study Summary

This will be an open-label, CRM-directed, dose-escalating Phase I safety trial conducted at a single site (UAB) in patients with a confirmed diagnosis of progressing MG after TMZ chemoradiation therapy. Treatment will be administered on an inpatient basis. Expected adverse events caused by M032 are described in **Section 5**. No investigational or commercial agents or therapies other than those described below may be administered with the intent to treat the patient’s malignancy.

These subjects will include eligible patients for whom surgical resection of their recurrent glioma is considered to be infeasible or would not likely afford greater benefit than the potential risks associated with surgical resection. All patients will be required to be placed on an anticonvulsant at the time of screening; those patients already on an anti-convulsant (anti-epileptic drug/AED) will have a second anti-convulsant added per the discretion of the investigator. This anti-convulsant will be continued for a minimum of 28 days unless the patient develops a reaction to the medication. If this develops, all attempts will be made to implement an alternative agent. On Day 0, these subjects will be treated under monitored local anesthesia, or at the surgeon’s discretion, under general anesthesia. The patients will undergo a contrasted MRI scan to determine the site(s) for stereotactic biopsy and inoculation of the test agent. Patients will then undergo stereotactic biopsy of their tumor. While evidence of radiation damage or necrosis may be present on the frozen section, inoculation with M032 will only proceed if viable, recurrent glioma is also present on the frozen section.

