8. STUDY CALENDAR

	Pre-Study (within 2 weeks prior to the administration of M032)	Day 0	Day1	Day 2	Day 3	Day 10 (± 3 days)	Day 28 (± 4 days)	Month 2 (± 12 days)	Month 3 (± 12 days)	Months 4, 5 (± 12 days)	Months 6, 9, 12 (± 12 days)	Unscheduled ²⁰
Informed consent	X ¹											
Inclusion/ Exclusion Criteria	X											
Demographics	X											
Pregnancy test-serum ⁴	X											
Medical history	X											
Concurrent meds	X	X	X	X	X	X	X	X	X	X	X	X
Complete physical exam (including wound assessment Days 1-10)	X		X	X ¹⁷	X ¹⁷	X	X		X		X	X ²¹
Vital signs	X	X	X ²	X ²	X ²	X	X		X		X	X ²¹
KPS	X				X	X	X		X		X	X ²¹
CBC w/diff, plts	X			X		X	X	X	X	X	X	X
Serum chemistry ³ , PT/INR, PTT	X			X		X	X	X	X	X	X	X
HIV serology	X											
EKG	X											
CXR (AP and lateral)	X											
Urinalysis with micro	X											
Adverse event evaluation ^{11, 12}		X	X	X	X	X	X	X	X	X	X	X
MRI ⁵	X ¹³	X			X		X		X		X	X ²¹
Neurologic exam	X	X	X ⁶	X ⁶	X ⁶	X	X		X		X	X ²¹
HSV Ab titer ⁷	X					X	X		X		X	X
HSV detection (saliva, conjunctival secretions, blood) ⁸	X			X ¹⁸	X ¹⁸ blood only	X	X	X	X	X	X	X
IL-12 detection (serum) ⁹	X			X ¹⁸	X ¹⁸	X	X		X		X	X
Blood sample for LTA, Elispot	X			X ¹⁸	X ¹⁸	X	X		X		X	X
IFN gamma assay	X			X ¹⁸	X ¹⁸	X	X		X		X	X
Blood to be stored for future immune studies	X	X ¹⁵		X ¹⁸	X ¹⁸	X	X		X		X	X
Head CT		X ¹⁰										

	Pre-Study (within 2 weeks prior to the administration of M032)	Day 0	Day 1	Day 2	Day 3	Day 10 (± 3 days)	Day 28 (± 4 days)	Month 2 (± 12 days)	Month 3 (± 12 days)	Months 4, 5 (± 12 days)	Months 6, 9, 12 (± 12 days)	Unscheduled ²⁰
Biopsy, Catheter placement		X										
Prophylactic AED	X	X	X	X	X	X	X ¹⁶					
M032 Administration			X									
Rickham/Ommaya reservoir aspiration ¹⁹	X	X	X	X	X	X	X		X		X	X ²¹

1. Will be obtained prior to study screening procedures.
2. Frequency post initiation of infusion: vital signs will be every hour for 12 hours post initiation, every 2 hours for the next 12 hours, then every 4 hours for the next 24 hours.
3. Includes sodium, potassium, chloride, bicarbonate, glucose, BUN, creatinine, calcium, phosphorus, total protein, uric acid, GGT, AST/ALT, CK, LDH, alkaline phosphatase, total bilirubin, cholesterol, triglyceride.
4. Only women of child-bearing potential. If necessary, can be repeated during the course of the study.
5. All MRI scans will be performed as prescribed by the Principal Investigator.

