6. Neurological exam includes assessment of cranial nerve abnormalities, gait abnormalities (when appropriate), sensory abnormalities, muscle strength, and level of consciousness. This will be evaluated every hour for 12 hours post initiation, every 2 hours for the next 12 hours, then every 4 hours for the next 24 hours.
7. By ELISA; neutralizing antibody assays may also be performed.
8. Samples will be evaluated by PCR and culture; quantitative PCR may be performed on positive samples.
9. IL-12 detection (serum) by ELISA.
10. After catheter placement but before start of infusion; may also take place on Day 1.
11. All AEs will be assessed throughout the course of the study, but specific CRFs will only be required at the time points delineated in the above schedule.
12. All unresolved toxicities be followed regularly by the treating physician and/or research coordinator; the nurse coordinator will conduct follow-up weekly with the subject, family and/or referring physician (by phone if travel is too burdensome for the subject) until resolution of treatment-related toxicity to less than Grade 2 (or Grade 3 if that was the subject's baseline).
13. MRI's that have been obtained within 30 days of pre-study visit may be used at the discretion of the PI.
14. Sample will be stored for future brain tumor research.
15. To be obtained post-op.
16. Prophylactic AED's may be discontinued at the Day 28 visit.
17. Wound examination only.
18. Acceptable up to 2 days after
19. Should a patient have an access device (eg., Rickham or Ommaya reservoir) that accesses either the more central portion of the tumor/cyst, or the CSF space, fluid will be aspirated as possible (expected, 2-10cc) from the catheter for laboratory studies. These specimens will be obtained at either the pre op clinic visit or the day of surgery, as well as up to daily during the inpatient hospitalization (per the surgeon's discretion), and again at post op visit day 10, Day 28, and Months 3,6,9 and 12.
20. If a participant is to miss a regularly scheduled research follow-up visit, an unscheduled visit can be conducted to capture research data at an otherwise standard of care clinic visit.
21. Collected only if done during an otherwise non-research visit (i.e., unscheduled visit).

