Day 0 (biopsy and catheter placement)

- Admit to the hospital for biopsy surgery and if eligible, catheter placement
- Review medications
- AE monitoring
- Obtain vital signs (pulse, blood pressure, respiratory rate, temperature and weight) prior to surgery
- Perform a neurological (nervous system) examination to include assessment of cranial nerve abnormalities, gait abnormalities (when appropriate), sensory abnormalities, muscle strength, and level of consciousness
- Obtain a stereotactic MRI to determine site for the biopsy and catheter placement
- Perform the biopsy and, if eligibility criteria are met, place and label up to 4 catheters

- Prime each catheter with 0.4 ml sterile saline solution and cap the catheters
- Admit to the Neurosurgery Intensive Care Unit for routine post-biopsy care and observation
- Obtain CT scan to ensure the catheters are in the proper position. (May be completed on Day 1 prior to drug administration)
- Collect blood for the following:
 - Immune studies - to be stored for future research – collect post-op
- Should a patient have an access device (eg., Rickham or Ommaya reservoir) that accesses either the more central portion of the tumor/cyst, or the CSF space, fluid will be aspirated as possible (expected, 2-10cc) from the catheter for laboratory studies. These specimens will be obtained at either the pre op clinic visit or the day of surgery, as well as up to daily during the inpatient hospitalization (per the surgeon's discretion), and again at post op visit day 10, Day 28, and Months 3,6,9 and 12

Day 1 (drug administration):

- If subject's condition is stable, transfer to a Clinical Research Unit inpatient bed for drug infusion and monitoring
- Review medications
- Perform a complete physical exam including wound assessment
- If not completed on Day 0, obtain a CT scan to ensure the catheters did not move and are still in the proper place
- Obtain pathology report and verify diagnosis

- Administration of study drug which will take approximately 6 hours (may last up to 12 hours)
- Study Drug Administration
 - Acquisition of study drug and diluent
 - Store syringes in refrigerator (4° C) until needed
 - Flush infusion tubing with diluent provided by pharmacy
 - Connect syringe with study drug to infusion tubing
 - Prime with 4.6 ml of the diluted virus preparation making sure that any excess study drug is disposed according to Biosafety Level 2 procedure
 - Connect tubing to catheter

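### Response is measured from a screening MRI that may predate M032 by up to 44 days, against the plan's own 4-week limit, while each patient's Day 0 contrast MRI goes unused and the reference for progression is inconsistent

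*Combined protocol and SAP*

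**What the plan says.** Section 9.3 judges objective response by comparing a baseline MRI with follow-up scans at Day 3, Day 28 and Months 3, 6, 9 and 12. For patients treated by intratumoral inoculation, "the screening MRI will serve as the baseline MRI".

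Three places govern how old that scan may be:
- The study calendar (section 8) limits the pre-study column to the two weeks before M032.
- Footnote 13 of the calendar, repeated under Screening in section 8.1, adds that "MRI's that have been obtained within 30 days of pre-study visit may be used at the discretion of the PI".
- Section 9.2 says screening evaluations should be as close to treatment as possible and "never more than 4 weeks before the beginning of the treatment".

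A later scan exists for every patient. In section 4.1, on Day 0, "The patients will undergo a contrasted MRI scan to determine the site(s) for stereotactic biopsy and inoculation of the test agent". The Day 0 list in section 8.1 repeats it: "Obtain a stereotactic MRI to determine site for the biopsy and catheter placement". Infusion follows on Day 1. Eligibility criterion 3.1.7 already relies on that day's imaging for lesion size: "These parameters will be re-evaluated on imaging done on the day of catheter implantation". Section 9.3 gives it no role in response.

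The reference for progressive disease (PD) differs by section. Section 9.3 compares with baseline. Section 9.3.1 requires an increase above 25% but names no reference scan. Sections 9.3.3, 9.4.2 and 9.4.3 refer to the lowest measurement obtained after treatment began. Section 9.3.4 calls for repeat imaging and clinical assessment at 3 months when a scan looks like PD, and dates confirmed progression back to the first scan that met the criteria.

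**The concern.** Section 4.1 describes the population as having progressing malignant glioma, so tumors can be expected to grow between the screening scan and infusion. A baseline taken weeks earlier puts that growth on the post-treatment side of the comparison. Two consequences follow.

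- **Partial response.** The more-than-50% reduction is counted from a smaller, older tumor, so more true shrinkage is needed to qualify. Complete response, defined by disappearance, does not depend on baseline size.
- **Progression and PFS.** If PD is judged from the 9.3 baseline, part or all of the 25% increase may have occurred before dosing, and the back-dating in 9.3.4 can then fix an early progression date.

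Scan age varies between patients, so the distortion does too. Section 9.2 treats imaging as the sole measure of antitumor effect, and section 4.1.1 lets PFS or OS inform the phase II dose if no MTD is reached.

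**Working it through.** **Step 1. Age of the baseline scan.** The plan's own limit is 4 weeks = 28 days (9.2). The calendar and footnote 13 give 14 days (visit to M032) + 30 days (scan to visit) = 44 days. The excess is 44 − 28 = 16 days, so the two rules cannot both stand. The Day 0 scan is about 1 day before infusion.

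**Step 2. Growth before treatment.** The documents give no growth rate. Assume exponential volume growth with doubling time DT, and let A be scan age in days.
- Growth factor at infusion: G = 2^(A/DT).
- Growth alone exceeds 25% by volume when DT < A × ln 2 / ln 1.25 = 3.106 × A.
- Section 9.3 mentions both areas and volumes. If the 25% is an area, the volume factor is 1.25^1.5 and the limit is DT < A × ln 2 / (1.5 × ln 1.25).
- True shrinkage from treatment-day volume needed for a partial response by volume: more than 1 − 0.5/G.

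The last two columns use assumed doubling times of 50 / 100 / 200 days.

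| Scan age A | DT limit, volume | DT limit, area | Pre-treatment growth | True shrinkage needed for PR |
|---|---|---|---|---|
| 44 days | 136.7 days | 91.1 days | 84.0% / 35.7% / 16.5% | 72.8% / 63.1% / 57.1% |
| 28 days | 87.0 days | 58.0 days | 47.4% / 21.4% / 10.2% | 66.1% / 58.8% / 54.6% |
| 14 days | 43.5 days | 29.0 days | 21.4% / 10.2% / 5.0% | 58.8% / 54.6% / 52.4% |
| 1 day (Day 0) | 3.1 days | 2.1 days | 1.4% / 0.7% / 0.3% | 50.7% / 50.3% / 50.2% |

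**Step 3. Effect on the PFS date, if PD is judged from the 9.3 baseline.** Take DT = 100 days, growth unaffected by treatment, and the steroid and neurologic conditions for PD met. Day 3 is 2 days after infusion and Day 28 is 27 days after it.
- 44-day scan: at Day 3, 2^(46/100) − 1 = 37.6%. The threshold is already passed at Day 3.
- 28-day scan: at Day 3, 2^(30/100) − 1 = 23.1%; at Day 28, 2^(55/100) − 1 = 46.4%. First passed at Day 28.
- 14-day scan: at Day 28, 2^(41/100) − 1 = 32.9%. First passed at Day 28.
- Day 0 scan: at Day 28, 2^(28/100) − 1 = 21.4%; at Month 3 (about 90 days), 2^(90/100) − 1 = 86.6%. First passed at Month 3.

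Once progression is confirmed, 9.3.4 assigns it to that first scan. The same tumor is therefore dated Day 3, Day 28 or Month 3 according to the age of its baseline scan.

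**Step 4. The other PD reference.** Under 9.3.3, 9.4.2 and 9.4.3 read literally, no pre-treatment scan can be the reference. The first candidate is Day 3, after biopsy, catheter placement and an infusion of about 2.4 ml. Growth before dosing is then excluded, but the starting measurement follows surgery and infusion. Neither reading uses the clean scan taken on Day 0.

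**The case against.** A reader might infer that pre-treatment growth is counted as progression after M032. The documents do not support that as a definite statement. Three sections take their PD reference from measurements made after treatment began, and section 9.3.1 names none. Section 9.3.4 also means one scan does not settle PD: enlargement that happened before dosing and does not continue would not meet its wording for confirmed progression. What stands is conditional. If the 9.3 baseline governs, growth can contribute to the threshold, and once progression is confirmed the date goes back to the first scan.

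A reader might also treat 44 days as the operative maximum. It is the outcome of a discretionary footnote that 9.2 contradicts. At the 28-day cap, a 100-day doubling time gives 21.4% growth, below the threshold; at 14 days even a 50-day doubling time gives 21.4%. These points reduce the size of the problem but do not remove it: partial response still needs more true shrinkage at 28 or 14 days than from Day 0.

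Two further points are fair. Response and PFS are secondary, descriptive endpoints in an uncontrolled trial of 8 to 24 patients, and the bias described tends to understate benefit rather than create a false signal. And the Day 0 scan is a targeting MRI, with scans left to the Principal Investigator's prescription (calendar footnote 5), so comparability with follow-up cannot be assumed. That is a condition on the fix, not a reason to keep the older scan.

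**Conclusion.** The point holds in conditional form. The 44 versus 28 day contradiction is certain from the text, as are the unused Day 0 scan and the inconsistent PD reference. Understatement of partial response follows from section 9.3 whenever the tumor grows between screening and infusion: with a 100-day doubling time, more than 63% true shrinkage is needed for a 44-day scan and 59% for a 28-day scan, against just over 50% from Day 0. An effect on PD and PFS arises only if the 9.3 baseline is the PD reference, which the plan leaves open.

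All growth figures assume exponential volume growth at rates the documents do not supply. Only response and PFS are affected; the DLT and MTD endpoint is not. The change should be made, but it does not threaten the trial's primary purpose.

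**What to change.** - In 9.3, name the Day 0 pre-biopsy contrast MRI as the baseline for response and progression, acquired and segmented with the same technique as the follow-up scans, as 9.2 already requires. Keep the screening MRI as fallback only when the Day 0 images are unusable.
- State one PD reference, the smallest measurement including the Day 0 baseline, in 9.3, 9.3.1, 9.3.3, 9.4.2 and 9.4.3.
- Reconcile footnote 13 and its repeat in 8.1 with the 4-week limit in 9.2.

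No additional scan is needed. The cost is consistent edits to these sections, because changing 9.3 alone would leave the progression reference contradictory. The practical burden is that the Day 0 targeting scan must be acquired so that it is comparable with follow-up.
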